10.5.5 Pharmacokinetics

[figure not shown]
All patients in PAS will be included in the PK data analysis.

Pharmacokinetic variables:

The PK parameters listed in [Table 10-2](#) for LEE011 will be estimated and reported as appropriate from the individual plasma concentration versus time profiles using a non-compartmental approach within Phoenix[®] (Pharsight, Mountain View, CA). Exploratory PK analysis will be conducted using compartmental modeling as required.

Table 10-2 Non-compartmental pharmacokinetic parameters

AUC _{tau}	The AUC calculated to the end of a dosing interval (tau) following single dose or at steady-state (amount x time x volume ⁻¹)
C _{max}	The maximum (peak) observed plasma, blood, serum, or other body fluid drug concentration after single dose administration or at steady-state (mass x volume ⁻¹)
T _{max}	The time to reach maximum (peak) plasma, blood, serum, or other body fluid drug concentration after single dose administration or at steady-state (time)
CL/F	The apparent total body clearance of drug from the plasma (volume x time ⁻¹)
R _{acc}	Accumulation ratio
T _{1/2,eff}	Effective elimination half-life

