Primary Objective	Estimate the MTD and/or RDE of LEE011 as a single agent when administered orally to patients
Secondary Objectives	
Objective 1: Characterize the safety and tolerability of LEE011
 
Objective 2: Characterize pharmacokinetics of LEE011 and any clinically significant metabolites that may be identified
 
Objective 3: Assess the anti-tumor activity of LEE011

Study design	This is a two-part, phase 1 study, with a dose escalation part followed by an expansion part. The expansion part will start after the MTD/RDE has been determined. The expansion part will include 2 groups of patients, one restricted to MRT patients with either CNS or extra-CNS primary and the second including neuroblastoma patients. LEE011 will be administered orally, once daily for 21 days followed by a 1 week break (28-day cycle).
Population	Patients, aged 12 months to 21 years, with MRT or neuroblastoma
Inclusion criteria	
 • Confirmed diagnosis of MRT, neuroblastoma, or in the dose escalation part, other tumors with D-cyclin-CDK4/6-INK4a-Rb pathway abnormalities, that has progressed despite standard therapy or for which no effective standard therapy exists. • Age \geq 12 months and \leq 21 years • Patients with CNS disease should be on stable doses of steroids for at least 7 days prior to first dose of LEE011 with no plans for escalation. • In expansion part, patients must have at least one measurable disease as defined by RECIST v1.1. • Patients must have a Lansky (\leq 16 years) or Karnofsky ($>$ 16 years) score of at least 50. • Patients must have fully recovered from the acute toxic effects of all prior chemotherapy, immunotherapy, or radiotherapy prior to enrollment.

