6.1.1 Dosing regimen

[figure not shown]
LEE011 is provided to investigational sites in capsule, powder in bottle (PIB) or liquid forms for oral use. LEE011 will be taken orally, once a day for 21 consecutive days followed by a 7-day planned break.

LEE011 dose will be scaled by Body Surface Area (BSA). The dose will be adjusted to the nearest 10 or 50 mg (higher or lower) as appropriate. The investigational site staff will inform each patient of their actual daily dose, and this will be recorded on the appropriate eCRF. The actual dose for each patient will be calculated using a BSA conversion as follows:

Actual dose = planned dose level (mg/m²) x individual patient (to nearest 10 or 50 mg, BSA higher or lower as appropriate).

Individual patient BSA will be calculated using their height and weight as per standard site procedure. For the purpose of BSA calculations and potential dose readjustment at subsequent cycles, it is acceptable for the BSA to be calculated up to 7 days in advance of Day 1. Dosage adjustments for changes in BSA in subsequent cycles will be made as per standard site practice (e.g., if the BSA changes by ± 10% from the previous dose calculation).

For capsules, individual doses will consist of the minimum number of capsules possible given the available capsule sizes.

The investigator should instruct the patient to take the study drug exactly as prescribed below. All dosages prescribed and dispensed to the patient, and all dose changes during the study must be recorded on the appropriate eCRF.

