6.2 Dose escalation guidelines

6.2.1 Starting dose for the dose escalation part

The first cohort of patients in this trial will be treated with a dose of 280 mg/m²/d, which is 80% of the current well tolerated dose (600 mg/d) in the ongoing adult study [CLEE011X2101] divided by the average adult body surface area (BSA) of 1.72 m². Table 6-1 describes the starting dose and the dose levels that may be evaluated during this trial.

Table 6-1 Provisional dose levels

Dose level	Proposed daily dose*	Increment from previous dose	Corresponding adult dose level
-1 [°]	210 mg/m ²	-25%	360 mg/d
1 (starting dose)	280 mg/m ²	(starting dose)	480 mg/d
2	420 mg/m ²	50%	720 mg/d
3	630 mg/m ²	50%	1080 mg/d

This table is intended only as a guide. Values in table are examples and actual doses may vary.

* Additional dose levels may be added during the course of the study. Cohorts may be expanded at any dose level below MTD in order to better understand safety, PK or PD.

[°] Dose level -1 is a dose level that may be evaluated if the starting dose level is not well tolerated

Since the adult MTD has not been established, LEE011 doses higher than 630 mg/m² may be evaluated depending on the data from the adult Ph1 study and observed safety, PK and PD.

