10.5.5.2 Data analysis principles

Analysis sets

Only PK blood samples with date and time and for which the last prior dose dates and times are adequately recorded will be included in the PK analyses. Samples taken from patients who vomited within 4 hours of dosing will be excluded from the analysis.

Basic tables, figures and listings

The individual plasma concentration versus time profiles and mean concentration versus time profile of LEE011 and analyzed metabolites (if any) will be listed, summarized and displayed graphically.

Descriptive statistics of all pharmacokinetic parameters will include arithmetic and geometric mean, median, standard deviation (SD), and Coefficient of Variation (CV), geometric CV, minimum and maximum. However, for T_{max}, median values and ranges will be given. Zero concentrations will not be included in the geometric mean/CV calculation. Summaries by age group will also be provided as appropriate.

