10.8 Sample size calculation

Dose-escalation phase

Each cohort will enroll 3 to 6 evaluable patients, including at least six patients at the MTD/RDE level and a minimum of 12 patients in total (details in [Section 6.2.2](#)). Multiple cohorts may be sequentially enrolled to the same dose level. Additional cohorts of 1 to 6 patients may be enrolled at any dose level below the estimated MTD/RDE for further elaboration of safety and pharmacokinetic parameters as required. It is expected that approximately 10 patients may be enrolled and treated within this context. In all, it is anticipated that approximately 28 patients will be treated during the escalation phase for the model to have reasonable operating characteristics relating to its MTD recommendation.

Dose expansion part

During dose expansion a sample size of approximately 18 evaluable patients per arm (including those with MRT or neuroblastoma treated at the recommended MTD/RDE during dose-escalation) will be treated to gain more information about the overall safety and tolerability of LEE011, to provide additional PK and PD data to guide the selection of dosing for future studies with LEE011, and to provide an early opportunity to identify LEE011 anti-tumor activity associated with neuroblastoma and MRT populations.

Assuming no differences in toxicity profile across the subpopulations enrolled in the expansion phase, 36 patients will result in 97% probability of detecting at least one adverse event with a true rate of 10%. This probability rises as the true adverse event rate increases.

To allow for dropouts and expansion of cohorts, it is estimated that approximately 64 patients may be treated in the entire study.

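### CL/F is summarised only in absolute units although dosing is per m², so body-size mix inflates its CV and confounds comparisons between small dose groups; CL/F per m² should be added

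*Protocol*

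**What the plan says.** - **Dosing.** Protocol Section 6.1.1: "LEE011 dose will be scaled by Body Surface Area (BSA"). The mg dose is the planned mg/m² level times the patient's BSA, and "The dose will be adjusted to the nearest 10 or 50 mg (higher or lower) as appropriate".
- **Population.** The protocol summary gives "Patients, aged 12 months to 21 years, with MRT or neuroblastoma"; the escalation part also admits other tumours with pathway abnormalities.
- **Parameter.** CL/F is a named secondary PK endpoint (Table 3-1). Table 10-2 defines it as "The apparent total body clearance of drug from the plasma (volume x time", completed by the exponent −1). AUCtau and Cmax stand in the same table.
- **Summary.** Section 10.5.5.2: "Descriptive statistics of all pharmacokinetic parameters will include arithmetic and geometric mean, median, standard deviation (SD), and Coefficient of Variation (CV"), with geometric CV, minimum and maximum. Section 10 presents summaries by treatment group, that is by dose level, pooling cohorts at the same level. Age-group summaries are conditional and no age bands are defined. Compartmental modelling is exploratory and names no size covariate.
- **Not in the supplied documents.** CL/F per m² or per kg, dose-normalised AUCtau or Cmax, or any plot of clearance against BSA, weight or age.
- **SAP.** It covers the final CSR only, analyses no PK (Section 2.9) and leaves the primary-CSR analyses to RAP Module 3 (Section 1), which is not supplied.

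**The concern.** CL/F is dose divided by AUC, and here the mg dose is itself proportional to BSA. Within one mg/m² group, absolute CL/F varies with body size even when every patient has the same exposure. The age range makes that size range wide, and Section 10.8 sets escalation cohorts at 3 to 6 evaluable patients, too few for the size mix to average out between dose groups.

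The design leans on BSA equivalence. Section 6.2.1 sets the starting dose at "80% of the current well tolerated dose (600 mg/d) in the ongoing adult study", "divided by the average adult body surface area (BSA) of 1.72" m², and Appendix 7 expects the DLT probability at a mg/m² dose to resemble that at the corresponding adult flat dose. Clearance per m², set beside adult clearance per m², is a direct PK check on that premise. Section 10.8 also wants the expansion part "to provide additional PK and PD data to guide the selection of dosing for future studies with LEE011". A CL/F table whose CV and between-dose differences partly reflect who happened to be enrolled serves those uses poorly.

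**Working it through.** **Inputs from the documents.** Adult BSA 1.72 m² and 600 mg/d (Section 6.2.1); rounding to 10 or 50 mg (Section 6.1.1); cohorts of 3 to 6 (Section 10.8); BSA = 234.94 × height(cm)^0.422 × weight(kg)^0.515 / 10000 (SAP Section 2.3).

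**Assumptions.** The documents give no paediatric BSA distribution and no between-patient CV. I assume a 12-month-old of 75 cm and 10 kg (alternatively 72 cm and 8 kg), an upper BSA of 1.72 m², BSA log-uniform over the range, and CL/F proportional to BSA. The size-free CV is varied over 30%, 50% and 70%.

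**1. The plan's own BSA figure.** 0.8 × 600 / 1.72 = 279.07 mg/m², against 280 stated. Table 6-1 also reproduces: 210, 280, 420 and 630 × 1.72 = 361, 482, 722 and 1084 mg, against 360, 480, 720 and 1080.

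**2. How size enters.** With planned level D, dose = D × BSA. At steady state, CL/F = D × BSA / AUCtau, so CL/F per m² = D / AUCtau. For illustration, take D = 280 mg/m² and a true clearance of 40 L/h/m². AUCtau is 280/40 = 7.0 mg·h/L at any size, but CL/F is 40 × 0.48 = 19.2 L/h at 0.48 m² and 40 × 1.72 = 68.8 L/h at 1.72 m².

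**3. Size range.** The formula gives 0.476 m² (75 cm, 10 kg) and 0.417 m² (72 cm, 8 kg). Against 1.72 m² the range is 3.6-fold and 4.1-fold.

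**4. Effect on the CV.** For a 3.6-fold range the SD of log BSA is s = ln(3.6)/√12 = 0.370, so s² = 0.137. The size share of log-variance is s² / (s² + ln(1 + CV²)), and the CV of absolute CL/F is √(exp(s² + ln(1 + CV²)) − 1).

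| Size-free CV | ln(1 + CV²) | Size share | CV of absolute CL/F |
|---|---|---|---|
| 30% | 0.086 | 61% | 50% |
| 50% | 0.223 | 38% | 66% |
| 70% | 0.399 | 26% | 84% |

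Size is more than half of the variance only if the size-free CV is below √(exp(0.137) − 1) = 38%. That threshold runs from 27% to 43% for BSA ranges of 2.5- to 4.2-fold.

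**5. Effect on a comparison of two dose groups.** Approximate 95% limits on the ratio of geometric means, with no true difference, are ×/÷ exp(1.96 √(2V/n)). V is s² + ln(1 + CV²) for absolute CL/F and ln(1 + CV²) for CL/F per m².

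| Size-free CV | n = 3 each: absolute / per m² | n = 6 each: absolute / per m² |
|---|---|---|
| 30% | 2.13 / 1.60 | 1.71 / 1.39 |
| 50% | 2.61 / 2.13 | 1.97 / 1.71 |
| 70% | 3.23 / 2.75 | 2.29 / 2.04 |

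**6. What AUCtau leaves over.** By step 2, AUCtau within a dose group is D / (CL/F per m²), except where the actual dose departs from D × BSA. At 0.48 m², 280 mg/m² is 134.4 mg: rounding to 130 mg changes the dose by −3%, and to 150 mg by +12%. BSA drift between dose recalculations adds to this. It should be small for the full profiles, which Table 7-4 places in Cycle 1.

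**The case against.** The strongest reply is that Table 10-2 already contains AUCtau and Cmax. Tabulated by mg/m² level, AUCtau is the proposed variable inverted and multiplied by D, apart from rounding and BSA drift. Dose-linearity can be read from it directly; the adult over-proportionality in Section 1.2.1.3 is itself stated in terms of exposure. AUCtau by age group would show whether BSA dosing equalises exposure. This largely stands, and it is why the point is confined to CL/F. What remains is that AUCtau is not normalised to the dose given, comparison across dose levels needs a normalisation the plan does not state, and the age-group summaries are optional.

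The other replies have force too:

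- Volume per time is the standard unit for CL/F, so the definition is not an error. Absolute CL/F can be compared with the predicted human value of 75.5 L/h (Section 1.2.1.1.2), and reporting only a per-m² value would presuppose that clearance scales with BSA. This stands, so the new parameter should be added and not substituted.
- Very small groups stay imprecise in either unit: at a size-free CV of 50% and n = 3, the limits are still ×/÷2.13 per m². Groups may also grow by pooling. This stands, but the per-m² limits are tighter in every row above.
- The endpoint list in Table 3-1 is open-ended, and actual dose and BSA are recorded, so CL/F per m² can be derived later. True, but the supplied documents do not plan it.
- RAP Module 3 may already contain it. That cannot be checked here, so the recommendation is conditional.

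**Conclusion.** The point holds as a minor gap in a secondary, descriptive analysis. Summarising CL/F only in absolute units lets size mix inflate its CV and confound comparisons between small dose groups, and the supplied documents plan no check of clearance against size. Under the assumed 3.6-fold BSA range, size accounts for about 26% to 61% of the log-variance for a size-free CV of 70% to 30%. With six patients per group, adding CL/F per m² tightens the 95% limits from ×/÷1.71 to ×/÷1.39 at CV 30%, and from ×/÷1.97 to ×/÷1.71 at CV 50%. These figures rest on assumed body sizes, log-uniform BSA and proportional scaling; the step 2 identity does not.

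A reader might infer two stronger things. One is that the CL/F tables would mainly show body size; that needs a size-free CV below about 38%, which the documents do not give. The other is that the plan cannot show dose-linearity or whether BSA dosing works; AUCtau and Cmax by dose group, with age-group summaries where provided, address both to a large extent. Neither inference is supported. The primary DLT/MTD analysis does not use CL/F and is unaffected.

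**What to change.** In Table 10-2 and Section 10.5.5.2, or in the primary-CSR RAP Module 3 unless it already does so:

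1. Add CL/F per m² = (actual dose given / BSA used for that cycle) / steady-state AUCtau, in L/h/m², summarised by dose group beside absolute CL/F. Keep absolute CL/F in the summaries.
2. Plot CL/F and CL/F per m² against BSA and against age. The first plot shows whether clearance scales with BSA; the second shows any residual trend.

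The cost is one derived variable, extra summary rows and a small set of plots. Table 7-1 already schedules height, weight and BSA at screening and on Day 1 of each cycle, and the actual dose is recorded on the eCRF, so no new data are needed.

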10.5.5.1 Data handling principles

All samples will be assayed for LEE011 concentrations by Novartis using methods that will be fully described in the CSR. Values below the assay LLOQ will be reported as 0.00 ng/mL. Missing values will be labeled accordingly.

10.5.5.2 Data analysis principles

Analysis sets

Only PK blood samples with date and time and for which the last prior dose dates and times are adequately recorded will be included in the PK analyses. Samples taken from patients who vomited within 4 hours of dosing will be excluded from the analysis.

Basic tables, figures and listings

The individual plasma concentration versus time profiles and mean concentration versus time profile of LEE011 and analyzed metabolites (if any) will be listed, summarized and displayed graphically.

Descriptive statistics of all pharmacokinetic parameters will include arithmetic and geometric mean, median, standard deviation (SD), and Coefficient of Variation (CV), geometric CV, minimum and maximum. However, for T_{max}, median values and ranges will be given. Zero concentrations will not be included in the geometric mean/CV calculation. Summaries by age group will also be provided as appropriate.

10.6 Exploratory objectives

For exploratory objectives, refer to [Table 3-1](#).

[figure not shown]
10.6.1 Biomarkers

10.6.1.1 Outline of the data analysis

Since this clinical trial was not designed to address specific biomarkers-related hypotheses, the analysis of this data should be viewed as exploratory and hypotheses generating.

There may be circumstances when a decision is made to stop collection, or not to perform or discontinue the analysis of samples due to either practical or strategic reasons. Under such circumstances, the sample size number may be too small or the quality of the data not sufficient to perform any data analysis and the available data will be only listed.

Additional analyses that may be performed after the completion of the end-of-study CSR will be documented in separate reports. These analyses may include but are not limited to the meta-analysis of data from this study combined with data from other studies or the analysis of biomarkers generated from samples collected during the study but analyzed after the database lock and completion of the CSR. The data analysis will be described in a stand-alone analysis plan document, as appropriate.

10.6.1.2 Data handling principles

All measurements below their respective LLOQs or missing data will be labeled as such in the data listings. Imputation rules for measurements below the LLOQ will be described in the RAP.

Details of the data handling principles will be specified in the RAP. These will include definition of MYCN mutation (neuroblastoma) and [REDACTED] amplification (MRT) cutoff for gene copy numbers.

10.6.1.3 Data analysis principles

10.6.1.3.1 Analysis sets

FAS will be used for biomarker related analysis

10.6.1.3.2 Basic tables, figures and listings

Relationship between MYCN (neuroblastoma), [REDACTED] (MRT), other genetic alterations and anti-tumor activity at the MTD/RDE will be presented using two way tables of best overall response. Moreover, the panel of assessed genes known to be genetically altered at a frequency of at least 5% in our study population will also be listed.

Pharmacodynamic assessments of LEE011 will be evaluated by pre and post treatment bone marrow aspirate/biopsy samples analyzed for [REDACTED] and [REDACTED]. Absolute and/or relative (%) changes from baseline will be listed by subject and summarized using descriptive statistics by treatment and by visit for each biomarker. Longitudinal plots showing patient level and mean changes may also be generated.

[REDACTED] collected from archival tumor samples will be listed.

10.6.1.3.3 Advanced analysis methods

Additional analyses of biomarker data may be performed as needed. These will be documented in the RAP or a stand-alone analysis plan document.

[figure not shown]
10.6.2 PK-QTc relationship

Matched PK and ECG data will be used to investigate any possible relationship between LEE011 exposure (as measured by PK assessments of LEE011 plasma concentration) and QT prolongation.

To investigate the possible relationship between LEE011 concentration and change from baseline in QTcF, hereafter denoted Δ QTcF, different mixed effect models will be fitted (Table 10-3). The initial model contains only two explanatory variables, baseline QTcF and LEE011 concentration. This allows a first assessment of any possible relationship between LEE011 concentration and Δ QTcF, but without controlling for the possible confounding effects of other factors. Model 2 will be augmented with Day and Day*LEE011 concentration interaction term. If the interaction term will be non-significant it will be removed from the model before proceeding to the subsequent exploratory model in which different number of covariates of interest will be considered for inclusion (details specified in the RAP). Moreover,

[REDACTED]

additional models such as mixed effect model with correlation and non-linear mixed model may be used if appropriate.

Central tendencies

For each treatment group, mean Δ QTcF will be evaluated by time point, and the maximum mean Δ QTcF identified. A plot will be produced showing maximum mean Δ QTcF (with SD) versus dose group. This will make possible the review of the data for indication of a relationship between dose and maximum mean Δ QTcF.

A plot will be produced of mean Δ QTcF and standard error (SE) by scheduled time point representing each treatment group on the same axes. This allows the data to be reviewed for indication of a dose effect on the magnitude of mean Δ QTcF, or on the time of maximum mean Δ QTcF.

[figure not shown]
Investigation of lagged effect

The relationship between T_{max} and the time of maximum Δ QTcF will be investigated graphically. For each treatment group, plots of mean LEE011 concentration by time and of mean Δ QTcF will be plotted on the same axes, using the matched ECG and PK concentration data.

10.7 Interim analysis

No formal interim analyses are planned. However, the dose-escalation design foresees that decisions based on the current data are taken before the end of the study. More precisely, after each cohort in the dose-escalation phase, the next dose will to be chosen depending on the observed data. Details of this procedure and the process for communication with investigators are provided in [Section 6.2.2](#).

Additionally, upon completion of the first cycle of treatment for at least 10 patients within the dose expansion part, if the observed DLT rate exceeds 33%, the BLRM will be re-run to confirm that the estimated MTD/RDE still satisfies the overdose criteria of the model.

